12.4. Appendix 4: Study Phases and Treatment Emergent Adverse Events

12.4.1. Study Phases

Assessments and events will be classified according to the time of occurrence relative to study treatment start date.

Study Phase	Definition
Pre-Treatment	Date ≤ Study Treatment Start Date
On-Treatment	Study Treatment Start Date < Date ≤ Study Treatment Stop Date + 28 days
Post-Treatment	Date > Study Treatment Stop Date + 28 days

Completion of study epochs will be defined as the following:

Study Phase	Definition of Completion
Run-in	Randomised into study and received first dose of study treatment
Treatment	Completed Week 12 visit
Follow up	Completed 12 week follow-up period

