12.4.2. Study Phases for Concomitant Medication

Study Phase	Definition Note: All programming should use start and end dates where available, CMSTRF and CMENRF are only to be used where dates are unavailable to help determine the correct study phase.
Pre-Treatment	
 Conmed Start Date < Study Treatment First Dose Date Conmed End Date < Study Treatment First Dose Date CMSTRF = "BEFORE" Randomisation date is missing i.e. subject was not randomised
On-Treatment	
 Study Treatment First Dose Date ≤ Conmed Start Date ≤ Study Treatment Last Dose Date + 28 Study Treatment First Dose Date ≤ Conmed End Date ≤ Study Treatment Last Dose Date + 28 (Conmed Start Date ≤ Study Treatment Last Dose Date + 28) and (Conmed End Date ≥ Study Treatment First Dose Date) (Conmed Start Date ≤ Study Treatment Last Dose Date + 28) and (CMENRF = "DURING/AFTER" or CMENRF = "AFTER" or CMSTRF = "DURING") (CMSTRF = "BEFORE" or CMSTRF = "DURING" or CMENRF = "DURING/AFTER") and (Conmed End Date ≥ Study Treatment First Dose Date) (CMSTRF = "BEFORE" or CMSTRF = "DURING") and (CMENRF = "DURING/AFTER" or CMENRF = "AFTER") CMSTRF = "DURING" CMENRF = "DURING/AFTER"
Post-Treatment	
 Conmed Start Date > Study Treatment Last Dose Date + 28

Study Phase	Definition Note: All programming should use start and end dates where available, CMSTRF and CMENRF are only to be used where dates are unavailable to help determine the correct study phase.
	
 • Conmed End Date > Study Treatment Last Dose Date + 28 • CMENRF = "AFTER" • CMENRF = "DURING/AFTER"
All phases	
 • Conmed start date is missing and CMSTRF is missing and conmed end date is missing and CMENRF is missing

NOTES:

- The duration of a single concomitant medication can extend over multiple study phases
- Please refer to [Appendix 7: Reporting Standards for Missing Data](#) for handling of missing and partial dates for concomitant medication. Use the rules in this table if concomitant medication date is completely missing.

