12.4.3. Treatment Emergent Flag for Adverse Events

Flag	Definition
Treatment Emergent	
If AE onset date is on or after treatment start date & on or before treatment stop date + 28 days.
 
Study Treatment Start Date ≤ AE Start Date ≤ Study Treatment Stop Date + 28 days

NOTES:

- If the study treatment stop date is missing then the AE will be considered to be On-Treatment.

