12.7.2.1. Handling of Missing and Partial Dates

Element	Reporting Detail
General	
 • Partial dates will be displayed as captured in subject listing displays.
Adverse	
 • The eCRF allows for the possibility of partial dates (i.e., only month and year) to be

Events	
recorded for AE start and end dates; that is, the day of the month may be missing. In such a case, the following conventions will be applied for calculating the time to onset and the duration of the event:
 
 ○ Missing Start Day: First of the month will be used unless this is before the start date of study treatment; in this case the study treatment start date will be used and hence the event is considered On-treatment as per Appendix 4: Study Phases and Treatment Emergent Adverse Events. ○ Missing Stop Day: Last day of the month will be used, unless this is after the stop date of study treatment; in this case the study treatment stop date will be used. ● Completely missing start or end dates will remain missing, with no imputation applied. Consequently, time to onset and duration of such events will be missing.
Concomitant Medications/ Medical History	
 ● Partial dates for any concomitant medications recorded in the CRF will be imputed using the following convention: 
 ○ If the partial date is a start date, a '01' will be used for the day and 'Jan' will be used for the month ○ If the partial date is a stop date, a '28/29/30/31' will be used for the day (dependent on the month and year) and 'Dec' will be used for the month. ● The recorded partial date will be displayed in listings.

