12.10.6. Safety Tables

Safety: Tables					
No.	Population	IDSL / Example Shell	Title	Programming Notes	Deliverable [Priority]
Adverse Events (AEs)					
3.01.	SAFF	SAFE_T01	Overview of On-treatment Adverse Events During the Study		SAC
3.02.	SAFF	AE1	Summary of All On-treatment Adverse Events by System Organ Class and Preferred Term	ICH E3	SAC
3.03.	SAFF	AE1	Summary of All On-treatment Serious Adverse Events by System Organ Class and Preferred Term	ICH E3	SAC
3.04.	SAFF	AE3	Summary of All On-treatment Adverse Events by Overall Frequency	ICH E3, summarise by PT	SAC
Laboratory: Chemistry					
3.05.	SAFF	LB1	Summary of Worst Case Chemistry Results Relative to Normal Range Post-Baseline Relative to Baseline	ICH E3	SAC
Laboratory: Hematology and Cardiac Markers					
3.06.	SAFF	LB1	Summary of Worst Case Hematology and Cardiac Markers Results Relative to Normal Range Post-Baseline Relative to Baseline	ICH E3	SAC

Safety: Tables					
No.	Population	IDSL / Example Shell	Title	Programming Notes	Deliverable [Priority]
ECG and Holter					
3.07.	SAFF	EG1	Summary of ECG Findings	IDSL	SAC
3.08.	SAFF	EG11	Summary of Maximum Increase in QTcF Values Post-Baseline Relative to Baseline by Category	IDSL	SAC
3.09.	SAFF	HM1	Summary of Holter Interpretations	IDSL	SAC
Vital Signs					
3.10.	SAFF	VS1	Summary of Vital Signs	ICH E3	SAC
3.11.	SAFF	VS1	Summary of Change from Baseline in Vital Signs	ICH E3	SAC
3.12.	SAFF	VS1	Summary of Change from Pre-dose to Post-dose in Vital Signs	ICH E3	SAC

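### An adverse event with no start date fails the treatment-emergent rule as written and is counted in none of the four AE tables, though it remains in the listings

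*SAP*

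**What the plan says.** Four parts of the SAP bear on this.

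- **Missing AE dates (12.7.2.1).** For a wholly absent date the rule is "Completely missing start or end dates will remain missing, with no imputation applied". The only effect it names is on timing variables: "Consequently, time to onset and duration of such events will be missing". Nothing is said about the treatment-emergent flag. Where only the start day is missing, the first of the month is used. If that falls before treatment start, the date moves to treatment start and the event counts as on-treatment.
- **Treatment-emergent flag (12.4.3).** The condition is "Study Treatment Start Date ≤ AE Start Date ≤ Study Treatment Stop Date + 28 days". One default is attached: "If the study treatment stop date is missing then the AE will be considered to be On-Treatment".
- **Study phases (12.4.1).** The on-treatment phase is "Study Treatment Start Date < Date ≤ Study Treatment Stop Date + 28 days".
- **AE tables (12.10.6).** Table 3.01 is titled "Overview of On-treatment Adverse Events During the Study". Tables 3.02 (by system organ class and preferred term), 3.03 (serious events) and 3.04 (by overall frequency) carry the same on-treatment restriction.

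**The concern.** The missing-date rule mentions time to onset and duration but not the more important consequence. An event without a start date has nothing to put into the flag, so it cannot qualify for a table limited to on-treatment events. Compared with counting such events, the omission works in one direction only: the tabulated numbers of AEs and SAEs can fall but cannot rise.

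The study now reports every endpoint descriptively (SAP 2.1 and 2.4), so these tables are its summary of adverse events, and section 12.5.2 keeps subject-level listings out of the main body of the report. Elsewhere the plan resolves doubt about AE timing towards on-treatment. The least informative AE date is the case left without that protection, which looks like an oversight.

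**Working it through.** The plan gives no figure to reproduce. The check is to follow an AE with a missing start date through the stated rules, and then to bound the effect.

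**Step 1. Date handling (12.7.2.1).** No date is imputed, so the start date stays missing.

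**Step 2. Flag (12.4.3).** The test is treatment start ≤ AE start ≤ treatment stop + 28 days. With AE start missing, neither inequality can be shown to hold, so the event is not flagged. The exception is a subject whose treatment stop date is also missing, where the note makes the AE on-treatment.

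**Step 3. Phase (12.4.1).** The on-treatment phase also needs a date, so it gives no other way in. The two sections differ on events dated on the day treatment starts, but that does not affect an undated event.

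**Step 4. Tables (12.10.6).** On-treatment tables: 3.01, 3.02, 3.03 and 3.04, which is 4 of 4. AE tables that would count the event: 0 of 4.

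**Step 5. Listings (12.10.9).** Listing 13 covers all AEs. Listings 17 to 21 cover fatal and non-fatal SAEs, reasons for seriousness, SAEs leading to withdrawal or discontinuation, and AEs of special interest. None is titled on-treatment, so an undated event still appears wherever it qualifies.

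**Step 6. Neighbouring rules.**

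| What is missing | Section | Result |
|---|---|---|
| AE start day, first of month before treatment start | 12.7.2.1 | On-treatment |
| Treatment stop date | 12.4.3 | On-treatment |
| All date information for a medication | 12.4.2 | All phases |
| Whole AE start date | 12.7.2.1 with 12.4.3 | Not flagged, not tabulated |

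**Step 7. Size.** SAP Table 1 says recruitment did not reach 20 randomised subjects, so at most 19. Assumption: roughly equal arms, since the SAP does not state the allocation. With 19 subjects the arms are 10 and 9.

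- The undated event is the subject's only event in the row: the change is 1/10 = 10.0 or 1/9 = 11.1 percentage points. Smaller arms give more.
- The subject has another on-treatment event in the same row: the change in the percentage of subjects is 0.
- If arms were very unequal, for example 18 in one of them, the change there would be 1/18 = 5.6 points.

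**The case against.** The plan nowhere says in words that undated AEs are excluded; this follows from applying its rules. Section 8.1 bases AE analyses on the sponsor's core data standards, and 12.5.2 applies its standards library unless otherwise stated. Either may hold a default that is not shown. That does not remove the point, because 12.4.3 and 12.7.2.1 set study-specific rules and do not defer to those standards for this case.

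Other objections stand and limit the point:

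- **Rarity.** The eCRF is described as allowing month and year without a day, and data cleaning precedes database release (3.1). A wholly missing start date should be uncommon.
- **Listings.** With so few subjects the listings are easy to read. A reader might infer that undated events vanish from the report. They do not; they are missing only from the tables.
- **Pre-treatment classification.** A reader might infer that SAS, which sorts missing values low, would place the event before treatment. That assumes unguarded code that the SAP does not show.
- **On-treatment status.** A reader might infer that an undated event must be on-treatment because AE review begins at the first-dose visit. The schedule does not support this. The last planned dose is Day 57, so the on-treatment phase ends near Day 57 + 28 = Day 85, while follow-up is at Day 169. SAEs related to study participation are also collected at the two visits before dosing.
- **Medication comparison.** The all-phases rule requires "Conmed start date is missing and CMSTRF is missing and conmed end date is missing and CMENRF is missing". A medication spans an interval, whereas an AE is placed by a single onset date. The difference is not a contradiction, and the comparison is only supporting evidence.

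**Conclusion.** The gap is real and of low severity. Following 12.7.2.1 and 12.4.3 as written, an AE or SAE with no start date is left out of all four AE tables unless the treatment stop date is also missing. That is the opposite of the plan's handling of a missing AE start day and of a missing treatment stop date, and it can only lower the tabulated counts.

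The effect on a row ranges from 0 to about 10 percentage points, or somewhat more in smaller arms. The upper figure assumes fewer than 20 randomised, roughly equal arms, and that the undated event is the subject's only one in that row. A reader might take 10 points as a minimum per event; it is not, because another event by the same subject in the row brings the change to 0. The number of affected events is not given and is probably small.

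**What to change.** Add one sentence to 12.4.3:

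> If the AE start date is completely missing, the AE is considered treatment emergent/On-treatment unless its end date is before the study treatment start date.

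Leave time to onset and duration missing, as 12.7.2.1 already provides.

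The cost is one sentence and one line of derivation code, with no change to data collection. The downside is that an occasional pre-dose or post-treatment event may be counted as on-treatment, so the AE counts may be slightly high. For safety tables that is the more acceptable direction of error, and it matches the plan's neighbouring AE rules.

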12.8. Appendix 8: Values of Potential Clinical Importance

Values of potential clinical importance will not be used in this study, instead normal reference ranges of “Low”, “Normal” and “High” will be used.

12.9. Appendix 9: Abbreviations & Trade Marks

12.9.1. Abbreviations

Abbreviation	Description
ACQ-5	Asthma Control Questionnaire
ADaM	Analysis Data Model
AE	Adverse Event
AFAD	Allergic Fungal Airway Disease
AIC	Akaike's Information Criteria
AQLQ	Asthma Quality of Life Questionnaire
ASE	All Subjects Enrolled
A&R	Analysis and Reporting
CDISC	Clinical Data Interchange Standards Consortium
CI	Confidence Interval
CPMS	Clinical Pharmacology Modelling & Simulation
CRO	Contract Research Organisation
CS	Clinical Statistics
CSR	Clinical Study Report
CTR	Clinical Trial Register
CV _b / CV _w	Coefficient of Variation (Between) / Coefficient of Variation (Within)
DBF	Database Freeze
DBR	Database Release
DOB	Date of Birth
DP	Decimal Places
ECG	Electrocardiogram
eCRF	Electronic Case Record Form
EOS	Eosinophils
FeNO	Fractional Exhaled Oxide
FEV1	Forced expiratory volume in 1 second
HARP	Harmonisation of Analysis and Reporting Program
IA	Interim Analysis
ICF	Informed Consent Form
ICH	International Conference on Harmonisation
IDMC	Independent Data Monitoring Committee
IDSL	Integrated Data Standards Library
IgE	Immunoglobulin E
IMMS	International Modules Management System
IP	Investigational Product
iSRC	Internal Safety Review Committee
ITT	Intent-To-Treat
GUI	Guidance
LOC	Last Observation Carries Forward
mITT	Modified Intent-To-Treat
MMRM	Mixed Model Repeated Measures
PCI	Potential Clinical Importance

Abbreviation	Description
PD	Pharmacodynamic
PDMP	Protocol Deviation Management Plan
PGx	Pharmacogenetic
PK	Pharmacokinetic
POC	Proof of Concept
PP	Per Protocol
QC	Quality Control
QTcF	Frederica's QT Interval Corrected for Heart Rate
QTcB	Bazett's QT Interval Corrected for Heart Rate
RAP	Reporting & Analysis Plan
RAMOS	Randomisation & Medication Ordering System
RTF	Rich Text Format
SAC	Statistical Analysis Complete
SAE	Serious Adverse Event
SDTM	Study Data Tabulation Model
SoC	Standard of Care
SOP	Standard Operation Procedure
ST2	Suppressor of Tumorigenicity 2
TA	Therapeutic Area
TFL	Tables, Figures & Listings
WOCBP	Woman of Child Bearing Potential
GSK	GlaxoSmithKline

12.9.2. Trademarks

Trademarks of the GlaxoSmithKline Group of Companies
None

Trademarks not owned by the GlaxoSmithKline Group of Companies
SAS

12.10. Appendix 10: List of Data Displays

All displays (Tables, Figures & Listings) will use the term 'Subjects' instead of "Participants".

12.10.1. Data Display Numbering

The following numbering will be applied for RAP generated displays:

Section	Tables	Figures
Study Population	1.1 to 1.n	1.1 to 1.n
Efficacy	2.1 to 2.n	2.1 to 2.n
Safety	3.1 to 3.n	3.1 to 3.n
Pharmacokinetic	4.1 to 4.n	4.1 to 4.n
Population Pharmacokinetic (PopPK)	5.1 to 5.n	5.1 to 5.n
Pharmacodynamic and / or Biomarker	6.1 to 6.n	6.1 to 6.n
Pharmacokinetic / Pharmacodynamic	7.1 to 7.n	7.1 to 7.n
Section	Listings	
ICH Listings	1 to x	
Other Listings	y to z	

12.10.2. Mock Example Shell Referencing

Non IDSL specifications will be referenced as indicated and if required example mock-up displays provided in [Appendix 10: List of Data Displays: Example Mock Shells for Data Displays](#).

Section	Figure	Table	Listing
Study Population	POP_Fn	POP_Tn	POP_Ln
Efficacy	EFF_Fn	EFF_Tn	EFF_Ln
Safety	SAFE_Fn	SAFE_Tn	SAFE_Ln
Pharmacokinetic	PK_Fn	PK_Tn	PK_Ln
Population Pharmacokinetic (PopPK)	POPPK_Fn	POPPK_Tn	POPPK_Ln
Pharmacodynamic and / or Biomarker	PD_Fn	PD_Tn	PD_Ln
Pharmacokinetic / Pharmacodynamic	PKPD_Fn	PKPD_Tn	PK/PD_Ln

NOTES:

- Non-Standard displays are indicated in the 'IDSL / Example Shell' or 'Programming Notes' column as '[Non-Standard] + Reference.'

12.10.3. Deliverables

Delivery	Description
SAC	Final Statistical Analysis Complete

12.10.4. Study Population Tables

Study Population Tables					
No.	Population	IDSL / Example Shell	Title	Programming Notes	Deliverable [Priority]
Subject Disposition					
1.01.	mITT	ES8	Summary of Subject Status and Reason for Study Withdrawal	ICH E3, FDAAA, EudraCT	SAC
1.02.	mITT	SD4	Summary of Treatment Status and Reasons for Discontinuation of Study Treatment	ICH E3	SAC
1.03.	mITT	ES4	Summary of Subject Disposition at Each Study Epoch	ICH E3	SAC
1.04.	ASE	ES6	Summary of Screening/Run-in Status and Reasons for Screen/Run-in Failure	Journal Requirements	SAC
1.05.	ASE	NS1	Summary of Number of Subjects by Country and Site ID	EudraCT/Clinical Operations	SAC
1.06.	mITT	NS1	Summary of Number of Subjects by Country and Site ID	EudraCT/Clinical Operations	SAC
Protocol Deviation					
1.07.	mITT	DV1	Summary of Important Protocol Deviations	ICH E3	SAC
1.08.	mITT	IE1	Summary of Inclusion/ Exclusion Deviations	ICH E3	SAC
Population Analysed					
1.09.	Enrolled	SP1	Summary of Study Populations	IDSL. Footnote on population summary table that Safety and mITT populations are the same.	SAC
Demographic and Baseline Characteristics					
1.10.	mITT	DM1	Summary of Demographic Characteristics	ICH E3, FDAAA, EudraCT	SAC
1.11.	Enrolled	DM11	Summary of Age Ranges	EudraCT	SAC
1.12.	mITT	DM5	Summary of Race and Racial Combinations	ICH E3, FDA, FDAAA, EudraCT	SAC

Study Population Tables					
No.	Population	IDSL / Example Shell	Title	Programming Notes	Deliverable [Priority]
Prior and Concomitant Medications					
1.13.	mITT		Summary of Anti-Fungal Medications at Screening		SAC
1.14.	mITT	MH4	Summary of Current Medical Conditions	ICH E3	SAC
1.15.	mITT	MH4	Summary of Past Medical Conditions	ICH E3	SAC
1.16.	mITT	POP_T01	Summary of Disease Duration and Exacerbation History		SAC
1.17.	mITT	CM1	Summary of On-treatment Concomitant Medications	ICH E3	SAC
1.18.	mITT	CM1	Summary of On-treatment Asthma Concomitant Medications	ICH E3	SAC

12.10.5. Efficacy Tables

Efficacy: Tables					
No.	Population	IDSL / Example Shell	Title	Programming Notes	Deliverable [Priority]
Primary Efficacy: Blood Eosinophils and FeNO					
2.01.	mITT	EX1	Summary of Exposure to Study Treatment	ICH E3	SAC
2.02.	mITT		Summary of Raw and Change from Baseline in Blood Eosinophils		SAC
2.03.	mITT		Summary of Raw and Change from Baseline in FeNO		SAC
Secondary Efficacy: Spirometry					
2.04.	mITT		Summary of Raw and Change from Baseline in FEV ₁		SAC
Secondary Efficacy: Patient Reported Outcomes					
2.05.	mITT		Summary of Raw and Change from Baseline in ACQ-5 Total Score		SAC
2.06.	mITT		Summary of ACQ-5 Responders		SAC
2.07.	mITT		Summary of Raw and Change from Baseline in AQLQ Total Score		SAC
2.08.	mITT		Summary of AQLQ Responders		SAC

12.10.6. Safety Tables

Safety: Tables					
No.	Population	IDSL / Example Shell	Title	Programming Notes	Deliverable [Priority]
Adverse Events (AEs)					
3.01.	SAFF	SAFE_T01	Overview of On-treatment Adverse Events During the Study		SAC
3.02.	SAFF	AE1	Summary of All On-treatment Adverse Events by System Organ Class and Preferred Term	ICH E3	SAC
3.03.	SAFF	AE1	Summary of All On-treatment Serious Adverse Events by System Organ Class and Preferred Term	ICH E3	SAC
3.04.	SAFF	AE3	Summary of All On-treatment Adverse Events by Overall Frequency	ICH E3, summarise by PT	SAC
Laboratory: Chemistry					
3.05.	SAFF	LB1	Summary of Worst Case Chemistry Results Relative to Normal Range Post-Baseline Relative to Baseline	ICH E3	SAC
Laboratory: Hematology and Cardiac Markers					
3.06.	SAFF	LB1	Summary of Worst Case Hematology and Cardiac Markers Results Relative to Normal Range Post-Baseline Relative to Baseline	ICH E3	SAC

Safety: Tables					
No.	Population	IDSL / Example Shell	Title	Programming Notes	Deliverable [Priority]
ECG and Holter					
3.07.	SAFF	EG1	Summary of ECG Findings	IDSL	SAC
3.08.	SAFF	EG11	Summary of Maximum Increase in QTcF Values Post-Baseline Relative to Baseline by Category	IDSL	SAC
3.09.	SAFF	HM1	Summary of Holter Interpretations	IDSL	SAC
Vital Signs					
3.10.	SAFF	VS1	Summary of Vital Signs	ICH E3	SAC
3.11.	SAFF	VS1	Summary of Change from Baseline in Vital Signs	ICH E3	SAC
3.12.	SAFF	VS1	Summary of Change from Pre-dose to Post-dose in Vital Signs	ICH E3	SAC

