
12.7. Appendix 7: Reporting Standards for Missing Data

12.7.1. Premature Withdrawals

Element	Reporting Detail
General	
 • Subject study completion (i.e. as specified in the protocol) was defined as completing the 12-week treatment period and three month safety follow up. • Withdrawn participants were not replaced in the study. • All available data from participants who were withdrawn from the study will be listed and all available planned data will be included in summary tables and figures, unless otherwise specified.

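### All four AE and SAE tables stop 28 days after treatment stop, so events that start in the 12-week safety follow-up get no count by arm

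*SAP*

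**What the plan says.** SAP 12.10.6 plans four adverse event tables. Table 3.01 is the "Overview of On-treatment Adverse Events During the Study", Table 3.02 the "Summary of All On-treatment Adverse Events by System Organ Class and Preferred Term" and Table 3.03 the "Summary of All On-treatment Serious Adverse Events by System Organ Class and Preferred Term". Table 3.04, by overall frequency, is also limited to on-treatment events.

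The upper end of that window appears in two places and is the same in both. SAP 12.4.1 defines the on-treatment phase as "Study Treatment Start Date < Date ≤ Study Treatment Stop Date + 28 days", and SAP 12.4.3 defines the treatment-emergent flag as "Study Treatment Start Date ≤ AE Start Date ≤ Study Treatment Stop Date + 28 days". The two differ at the lower end, in how they treat the first dosing day, but that does not matter here. SAP 12.4.1 goes on to define a post-treatment phase, "Date > Study Treatment Stop Date + 28 days". No AE or SAE table refers to it, and no AE table covers the whole study.

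The schedule in SAP 12.2.1 has dosing at Weeks 0, 4 and 8, an end-of-treatment visit at Week 12 and a follow-up visit at Week 24. SAP 12.7.1 defines study completion as "completing the 12-week treatment period and three month safety follow up".

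**The concern.** The safety objective in SAP 2.2 is set against placebo. All inferential analysis has been dropped (SAP 2.1 and 2.4), so descriptive tables by arm are the only between-arm safety output left. For clinical events, those tables end where the safety follow-up begins.

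Other safety data are treated differently. Vital signs (SAP 8.2) and anti-drug antibodies (SAP 8.4) are summarised at Week 24. The worst-case chemistry summary (SAP 8.3) covers results after baseline without a 28-day limit, and chemistry is sampled at Week 24.

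A serious infection or cardiovascular event in Week 16 would thus be a row in a listing and would be absent from every summary. In so small a study, one such event would visibly change the counts by arm.

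**Working it through.** **Inputs**
- Dosing days 1, 29 and 57; Week 12 = Day 85; Week 24 = Day 169; windows of ±3 days at Weeks 8 and 12 (SAP 12.2.1).
- Cut-off = treatment stop + 28 days (SAP 12.4.1 and 12.4.3).
- Treatment stop date: not defined in the SAP. I take it as the last dose, because the concomitant medication rules in SAP 12.4.2 use last dose date + 28. The alternative is tested below.

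**The plan's own figure.** SAP 12.4.1 gives a 12-week follow-up: 169 − 85 = 84 days = 12 weeks. It reproduces.

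**All three doses, nominal timing**
- Cut-off: 57 + 28 = Day 85, the nominal Week 12 visit.
- Not tabulated: 169 − 85 = 84 days (Days 86 to 169).
- Share of Days 1 to 169: 84/169 = 49.7%.
- Lost before Week 12: 85 − 85 = 0 days.

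**If treatment stop means Week 12**
- Cut-off: 85 + 28 = Day 113.
- Not tabulated: 169 − 113 = 56 days (Days 114 to 169), 56/169 = 33.1%.

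**Visit shifts.** Let the Week 8 dose shift by a days and the Week 12 visit by b days, each from −3 to +3. The Week 12 visit falls (85 + b) − (57 + a + 28) = b − a days after the cut-off. This is positive in 21 of the 49 combinations. The largest value is 3 − (−3) = 6 days: dose on Day 54, cut-off on Day 82, visit on Day 88.

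**Dosing stopped early, participant followed to Week 24**

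| Last dose | Cut-off | Days from cut-off to nominal Week 12 | Days from cut-off to Week 24 |
|---|---|---|---|
| Week 4 (Day 29) | Day 57 | 28 | 112 (112/169 = 66%) |
| Week 0 (Day 1) | Day 29 | 56 | 140 (140/169 = 83%) |

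These two rows are scenarios. They apply only to a participant who stops dosing and stays under observation.

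**The case against.** The strongest reply is that the tables do what the endpoint asks. SAP 2.2 names treatment-emergent adverse events, SAP 12.4.3 defines them, and Tables 3.01 to 3.04 report them. The 28 days also match the four weeks of coverage that SAP 12.6.2 assigns to each dose. This stands: the existing tables are not wrong, and the window needs no change. What is missing is a companion summary for the rest of the follow-up.

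A second reply is that nothing is hidden, and this also stands. A reader might infer that late events are lost, but Listings 13 (all AEs), 17 and 18 (fatal and non-fatal SAEs), 21 (AESIs) and 48 (deaths) are not limited to on-treatment events. With fewer than 20 randomised subjects they could be counted by hand. A planned table would give those counts and denominators directly.

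Some stronger readings are tempting but unsupported:
- **The cut contradicts the Treatment epoch.** The entry "Completed Week 12 visit" in SAP 12.4.1 is a criterion for having completed the epoch. Events are classified by the separate phase definitions.
- **Week 12 vital signs drop out of the summaries.** SAP 8.2 summarises Weeks 12 and 24, SAP 12.3.1 uses nominal visits, and SAP 12.10.6 lists no maximum/minimum vital-sign table.
- **The 28-day cut removes the AESI counts.** No AESI table is planned for any period, so this is a separate gap.
- **Week 24 sampling shows that the drug still acts.** Sampling PK, sST2 and antibodies at Week 24 shows only that the design looks for it.

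**Conclusion.** The point holds as a gap in coverage. It is not an error in the treatment-emergent tables. With all three doses on schedule, the last 84 of 169 days (about 50%) have no AE or SAE count by arm, or 56 days (about 33%) if the stop date means Week 12. Under either reading the post-treatment phase is defined but used by no AE table.

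Loss of events before Week 12 is conditional. It is zero at nominal timing with all doses given, at most 6 days through visit shifts, and 28 or 56 days if dosing ends early and the participant remains in the study.

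The conclusion rests on two assumptions: that treatment stop is the last dose, and that AEs are collected to Week 24. The second is inferred from the stated safety follow-up, because the columns spanned by the AE review row of the schedule cannot be read in the text available. Any comparison here means descriptive counts side by side. SAP 2.1 says that the 20 randomised subjects needed for the internal safety review were not reached, so the practical impact is modest. The change is still worth making because it costs little.

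**What to change.** Leave Tables 3.01 to 3.04 and the 28-day window as they are. Add to SAP 12.10.6, by arm and descriptively:
- a version of Table 3.02 (all AEs) and of Table 3.03 (SAEs) for events that start in the post-treatment phase of SAP 12.4.1 up to Week 24, or alternatively for the whole study from first dose to Week 24;
- a count of subjects with AESIs over the same period, using the groupings already set out in SAP 12.6.3.

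A post-treatment version should also show how many subjects in each arm were still under observation after the cut-off. One sentence in SAP 12.4 should say which date the treatment stop date is, since the size of the gap depends on it.

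The cost is two or three more tables from data already collected. No new data, no new phase definition and no change to the endpoint are needed.
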